4. STUDY POPULATION

4.1. Inclusion Criteria

Subjects must meet all of the following criteria to participate in the study:

- Males and females \geq 18 years of age
- Subjects with confirmed hematologic malignancies:
 - Phase 1:
 - High-risk MDS/CMML (defined as \geq 10% peripheral blood or marrow blasts and/or International Prognostic Scoring System [IPSS]³⁴ score \geq 1.5) and relapsed or refractory to prior therapy
 - AML relapsed or refractory to prior therapy, or \geq 60 years of age and not a candidate for other therapies
 - Phase 2a:
 - MDS/CMML, relapsed from, or refractory to prior HMA therapy; the latter defined as failure to achieve clinical remission (CR), partial remission (PR) or hematologic improvement (HI) after previous HMA therapy (\geq 4 cycles of azacitidine or decitabine), or progression during, or toxicity to, previous HMA therapy precluding further HMA treatment, and
 - Bone marrow blast count \geq 10% or peripheral blast count \geq 5%, or IPSS-R³⁵ score \geq 3.5
 - At least 3 weeks beyond the last chemotherapy, targeted anticancer agent, major surgery or experiment treatment and recovered from all acute toxicities (\leq Grade 1). *Hydroxyurea used to control peripheral blast counts is permitted up to Day 7 of treatment on study.*
 - Adequate performance status: Eastern Cooperative Oncology Group (ECOG) \leq 2
 - Adequate renal and hepatic function:
 - Creatinine \leq 2.0 mg/dL, or calculated creatinine clearance \geq 45 mL/minute per the Cockcroft-Gault formula
 - Total bilirubin \leq 2 times the upper limit of normal (ULN)
 - ALT and AST \leq 2 times ULN

- Negative serum pregnancy test within 14 days prior to first dose of study therapy for women of child-bearing potential (WCBP), defined as a sexually mature woman who has not undergone a hysterectomy or who has not been naturally post-menopausal for at least 24 consecutive months (i.e., who has had menses any time in the preceding 24 consecutive months). Sexually active WCBP and male subjects must agree to use adequate methods to avoid pregnancy (oral, injectable, or implantable hormonal contraceptive; tubal ligation; intra-uterine device; barrier contraceptive with spermicide; or vasectomized partner) throughout the study and for 28 days after the completion of the study treatment.
- Ability to provide written informed consent

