4.3. Discontinuation of Subjects

4.3.1. Procedures for Withdrawal

Any subject may be removed from study for the following reasons:

- Subject withdrawal of the informed consent
- Subject noncompliance
- An increasing or unexpected pattern of unacceptable toxicity
- Disease progression
- Investigator judgment when the well-being and best interest of the subject is compromised

Subjects experiencing unacceptable toxicity should be removed from the study once complete resolution of toxicity has been documented. Individual subjects may be discontinued from the study by the investigator or sponsor at any time if either determines that it is not in the best interest of the subject to continue.

Any subject who becomes pregnant during the study must be discontinued from the study immediately, but should be followed through delivery or termination of the pregnancy. Subjects should also notify the investigator if they become pregnant within 28 days following the last dose of study drug. FPHU/Westat also must be notified if a subject becomes pregnant on study.

If a subject is discontinued from the study before completing the specified duration of treatment, they should be encouraged to complete the end-of-study assessments and to agree to report any serious adverse events for 28 days following the last dose of study drug. The date the subject is withdrawn and the primary reason for discontinuation will be recorded on the case report form (CRF).

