6.1. Screening Procedures

The following evaluation includes standard tests are to be performed within 28 days of study treatment to determine subject eligibility.

- Administration of informed consent
- Medical history, physical examination and vital signs
- ECOG Performance Status
- Height and weight
- The following lab tests:
 - Hematology
 - Serum chemistry
 - Urinalysis
- Beta HCG for WCBP
- 12-lead ECG
- Review of concomitant medications
- Disease-specific assessment (BM aspirate)

6.2. Requirements During Treatment Cycle 1

6.2.1. *Cycle 1, Day 1*

- Abbreviated physical examination
- Vital signs
- ECOG Performance Status
- Weight
- The following lab tests:
 - Hematology, if not performed within the previous 24 hours
 - Serum chemistry, if not performed within the previous 24 hours
 - Urinalysis, if not performed within the previous 24 hours
- 12-lead ECG, pre-dose and approximately 3 hours post-dose (following morning dose only)
- Review of concomitant medications
- Assessment of adverse events
- For subjects on 21-day dosing schedules: Peripheral blood collection in heparin for PK and XMP assessments, pre-dose (any time), between 0.5-1 hr post-dose, and between 2-4 hr post-dose
- For subjects on 21-day dosing schedule: Dispense 21-day supply of FF-10501-01 study drug for Cycle 1
- Assessment for survival

6.2.2. *Cycle 1, Day 8 (+/- 1 day)*

- Vital signs
- The following lab tests:
 - Hematology
 - Serum chemistry
- Review of concomitant medications
- Assessment of adverse events
- Review subject medication diary for FF-10501-01 study drug
- Assessment for survival

6.2.3. *Cycle 1, Day 15 (+/- 1 day)*

- Vital signs
- The following lab tests:

- Hematology
- Serum chemistry
- 12-lead ECG, pre-dose and approximately 3 hours post-dose (following morning dose only)
- Review of concomitant medications
- Assessment of adverse events
- For subjects on 21-day dosing schedules: Peripheral blood collection in heparin for PK and XMP assessments, pre-dose (within 15 minutes prior to dosing), between 0.5-1 hr post-dose, and between 2-4 hr post-dose
- Assessment for survival

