6.3. Requirements During Treatment Cycles After Cycle 1 (Cycles 2, 3, 4, etc.)

6.3.1. Day 1 (+/- 3 days, except for pre-dose procedures; ECG)

- Abbreviated physical examination
- Vital signs
- ECOG Performance Status
- Weight

- The following lab tests (within 3 days of each cycle):
 - Hematology
 - Serum chemistry
 - Urinalysis
- 12-lead ECG, pre-dose and approximately 3 hours post-dose (following morning dose only)
- Review of concomitant medications
- Assessment of adverse events
- Assessment for survival
- For subjects on 21-day dosing schedule: Dispense 21-day supply of FF-10501-01 study drug for cycle

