Appendix D. Schedule of Study Procedures

Study Activity	Screening ^a	Treatment Cycle 1					Treatment Cycles after Cycle 1		Progression or Relapse	End of Study ^o	Long-Term Follow-Up ^p
		Day 1	Day 8 ^k	Day 15 ^k	Day 22 ^k	End of Cycle 1 ^l	Day 1 ^m	End of Cycle 3 ⁿ			
Signed ICD	X										
Medical history	X										
Physical examination	X	X ^j					X ^j			X	
Vital Signs	X	X	X	X	X		X			X	
ECOG Performance Status	X	X					X			X	
Height	X										
Weight	X	X					X			X	
Hematology ^b	X	X	X	X	X		X			X	
Serum chemistry ^c	X	X	X	X	X		X			X	
Urinalysis ^d	X	X					X			X	
Beta-hCG for WCBP	X										
12-lead ECG	X	X ^e		X ^e			X ^e			X	
Concomitant medications	X						Continuous				
Adverse Event assessment							Continuous				
Bone Marrow Aspirate ^f	X					X		X	X		
Disease Response Assessment ^g	X					X		X	X		
Peripheral blood for PK assessment ^h		X		X							
Peripheral blood for PD (XMP) assessment ^h		X		X							
Administration of FF-10501-01 ⁱ		BID x 21 days					BID x 21 days				
Assessment of survival		X	X	X	X	X	X	X	X	X	X

^a Screening to be performed within 28 days of Cycle 1, Day 1

^b Hematology collected at Screening, Days 1, 8, 15 and 22 of Cycle 1, Day 1 of each subsequent cycle (within 3 days of Day 1 of each subsequent cycle) and End of Study. See **Table 7** for tests to be conducted at each time point.

^c Serum chemistry collected at Screening, Days 1, 8, 15 and 22 of Cycle 1, Day 1 of each subsequent cycle (within 3 days of Day 1 of each subsequent cycle) and End of Study. See **Table 7** for tests to be conducted at each time point.

^d Urinalysis collected at Screening, Day 1 of Cycle 1, Day 1 of each subsequent cycle (within 3 days of Day 1 of each subsequent cycle) and End of Study. See **Table 7** for tests to be conducted at each time point.

^e ECGs performed pre-dose and approximately 3 hours post-dose (following morning dose only)

^f Bone marrow aspirate required at Screening; at end of Cycles 1 and 3, every 2 cycles thereafter, and at relapse/progression, unless peripheral blood absolute count is $\geq 5.0 \times 10^9$ cells/L. See **Table 7** for tests to be conducted at each time point.

^g Disease Response Assessment may include bone marrow assessment, hematology for blood counts, physical exam, etc.

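### No pregnancy test is scheduled after Screening, so the rule to discontinue a pregnant subject immediately has no scheduled trigger

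*Protocol*

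**What the plan says.** Protocol 4.1 makes a "Negative serum pregnancy test within 14 days prior to first dose of study therapy" an eligibility condition for WCBP. The Screening list in 6.1 carries the matching item, "Beta HCG for WCBP". The Appendix D row "Beta-hCG for WCBP" is marked in the Screening column only.

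The protocol also sets out prevention and response:

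- Section 4.1 requires contraception during the study and for 28 days after treatment. Section 4.2 excludes pregnant and breast-feeding women.
- Section 4.3.1 states: "Any subject who becomes pregnant during the study must be discontinued from the study immediately". It adds follow-up to the end of the pregnancy and notification of the sponsor side.
- The same section says: "Subjects should also notify the investigator if they become pregnant within 28 days following the last dose of study drug".

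On the hazard, section 1.2 reports positive teratology studies of SM-108 in mouse, rat and rabbit, and describes this as expected for a cytotoxic drug. Section 1.1 says FF-10501-01 has the same active ingredient. Section 1.6.3 reports chromosomal aberrations in vitro.

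**The concern.** The discontinuation rule in 4.3.1 can operate only once a pregnancy is known, and nothing scheduled after the first dose is designed to make it known. Under 5.3, treatment runs until progression, unacceptable toxicity or the subject's decision to stop. Under 6.3.1, the next 21-day supply is handed out on Day 1 of each cycle. A pregnancy that nobody yet suspects would not stop that supply. At stake is fetal exposure to a drug with a stated teratogenic signal. The gap lies in detecting a contraceptive failure; prevention is covered. No efficacy or safety estimate depends on it.

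**Working it through.** The plan gives no figure of its own to reproduce. The check is a reading of every place where a test could be scheduled, followed by simple arithmetic on time.

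**1. Where a pregnancy test appears**

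| Place | Pregnancy test |
|---|---|
| Protocol 4.1 and 6.1, before first dose | Yes |
| Protocol 6.2.1 to 6.2.5, Cycle 1 | None |
| Protocol 6.3.1, Day 1 of later cycles | None; the list under "The following lab tests (within 3 days of each cycle)" is hematology, serum chemistry and urinalysis |
| Protocol 6.3.2 and 6.4, response visits and progression | None |
| Protocol 6.5, End of Study | None; the same three panels |
| Protocol 6.6, long-term follow-up | None; survival only |
| Protocol 7.1.10, Table 7 | hCG is in no panel |
| Protocol Appendix D and footnotes | Screening only |
| SAP 4.3 | A listing of pregnancy tests, with no time point |

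Scheduled tests after the first dose: 0.

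**2. What else could detect a pregnancy**

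Day 1 of later cycles includes an "Abbreviated physical examination", adverse event review and medication review. None of these is a pregnancy test. Section 7.1.1 also leaves an uncomplicated pregnancy out of the adverse event definition, so adverse event review is not built to capture one. Section 1.7.2 lists fatigue and nausea among the commonest events, so early symptoms could be put down to the drug.

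**3. Time without a scheduled test**

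Formula: cycles × 28 days, counted from first dose and including rest days. Inputs are from section 1.7.2.

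- Median of 2 cycles (33 subjects, 25 of them AML): 2 × 28 = 56 days.
- Longest MDS disease control in this study, 17 cycles: 17 × 28 = 476 days, or 476 / 365 = 1.3 years. The source reports disease control, so equating it with time on treatment is an inference.

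The 17 cycles are specific to this study; section 1.7.1 reports a subject in the Japanese MDS study at 18 cycles and continuing. The longest course in this study, 28 cycles (28 × 28 = 784 days), was in AML, which Phase 2a does not enroll.

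**4. How many subjects an amendment could reach**

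- Upper bound: 68 planned − 33 treated = 35.
- If Phase 1 accrual is complete: 20 or fewer. Phase 2a is 20 subjects, and eligible Phase 1 subjects at the recommended dose and schedule count toward it (3.1, 3.2). Section 1.8 already fixes the Phase 2 regimen.
- In either case, add any subjects still on drug. The documents do not say how many of these are WCBP.

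**5. Intervals between tests if Day 1 and End of Study tests are added**

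- Screening test to Cycle 2 Day 1: the Screening test falls 0 to 14 days before first dose, so 28 + 0 = 28 to 28 + 14 = 42 days nominal; 42 + 3 = 45 at most with the visit window.
- Between later Day 1 tests: 28 days; with ±3 days at each end, 28 − 6 = 22 to 28 + 6 = 34. A 14-day delay gives 28 + 14 = 42 nominal. Section 5.4.2 permits longer delays after two cycles, so 42 is not a ceiling.
- Last Day 1 test to End of Study on the 21-day schedule: 20 days to the last dose + 28 = 48 days (43 to 53 with the ±5 day window), 28 of them off drug.

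A subject at the median of 2 cycles would be tested at Screening, Cycle 2 Day 1 and End of Study, at intervals of up to 42 and about 48 days nominal. Spacing of about 28 days begins only with a third cycle.

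**The case against.** The strongest reply is that the protocol already manages pregnancy risk: a recent negative serum test, exclusion of pregnant women, required contraception to 28 days after treatment, and a clear response if pregnancy occurs. No section contradicts another. The subgroup is unquantified and possibly empty, and no analysis changes. On that view, repeat testing is an optional extra layer.

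Most of this stands, and it limits the point to a safety improvement of low probability. It does not remove it, because every measure listed either prevents pregnancy or acts after it is known. None detects a contraceptive failure, and the harm would be serious and irreversible.

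A reader might go further and infer that the protocol neglects pregnancy prevention, that 4.3.1 conflicts with the schedule, or that sites will do no further tests. The documents support none of these. Prevention is explicit, the rule and the schedule can coexist, and unscheduled tests remain open to any investigator. Consent pages and the Investigator's Brochure were not available and may contain testing instructions, so the point concerns the protocol's schedule and not actual practice.

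**Conclusion.** The point holds as a gap in safety monitoring. There are no scheduled pregnancy tests after the first dose, for a drug whose active ingredient had positive teratology in three species and whose protocol calls for immediate discontinuation on pregnancy. It should be corrected because the remedy is cheap and the possible harm is severe, even though the chance of an event is low.

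The 56 and 476 days measure time without a scheduled test. They could be read as a pregnancy risk, or as the time a pregnancy would go unnoticed. Neither reading is supported: the documents give no count of WCBP and no contraceptive failure rate, and a pregnancy could be recognized clinically well before the next test. The 56-day figure also rests on a median over all subjects treated so far, mostly AML, so it is only a rough guide to Phase 2a.

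**What to change.** In the Beta-hCG row of Appendix D, add marks at Day 1 of each cycle after Cycle 1 and at End of Study, with this footnote: *WCBP only. Day 1 of each cycle after Cycle 1: serum or urine, negative result before study drug is dispensed. End of Study: serum or urine.* Add matching bullets to 6.3.1 and 6.5. In 4.3.1, add: *A positive test stops dosing that day pending serum confirmation.* Leave the Screening test as it is.

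No visit is added. Blood is already drawn at these visits, and Appendix D has "Urinalysis collected at Screening, Day 1 of Cycle 1, Day 1 of each subsequent cycle" as well as at End of Study. Added tests per WCBP are (cycles − 1) + 1 = the number of cycles: 2 at the median and 17 for the longest MDS course inferred above. The other costs are a short hold before dispensing (minutes with a urine test) and a protocol amendment with IRB approval and possible consent and CRF edits (9.4). The change can be bundled with the next amendment.

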4.2. Exclusion Criteria

Subjects who meet any of the following criteria will be excluded from the study:

- Known history of active coronary artery disease, angina, myocardial infarction, congestive heart failure, cardiac arrhythmia or any other type of heart disease present within the last 6 months
- Known family history of hereditary heart disease
- QT interval corrected for rate (QTc) > 450 msec on the electrocardiogram (ECG) obtained at Screening
- Concomitant medication(s) that may cause QTc prolongation or induce Torsades de Pointes with the exception of anti-microbials that are used as standard of care to prevent or treat infections and other such drugs that are considered by the Investigator to be essential for the care of the patient
- Presence of active central nervous system (CNS) leukemia. Subjects adequately treated for CNS leukemia documented by 2 consecutive cerebrospinal fluid samples negative for leukemia cells are eligible. Subjects with no history of CNS leukemia will not be required to undergo cerebrospinal fluid sampling for eligibility.
- Any other medical intervention or other condition which, in the opinion of the Principal Investigator, could compromise adherence with study requirements
- Known positive for human immunodeficiency virus (HIV), hepatitis B virus surface antigen (HBsAg), or hepatitis C virus (HCV)
- Active infection requiring intravenous (IV) anti-infective usage within the last 7 days prior to study treatment
- Pregnant or breast-feeding
- Treatment with any investigational product within 28 days prior to Screening

4.3. Discontinuation of Subjects

4.3.1. Procedures for Withdrawal

Any subject may be removed from study for the following reasons:

- Subject withdrawal of the informed consent
- Subject noncompliance
- An increasing or unexpected pattern of unacceptable toxicity
- Disease progression
- Investigator judgment when the well-being and best interest of the subject is compromised

Subjects experiencing unacceptable toxicity should be removed from the study once complete resolution of toxicity has been documented. Individual subjects may be discontinued from the study by the investigator or sponsor at any time if either determines that it is not in the best interest of the subject to continue.

Any subject who becomes pregnant during the study must be discontinued from the study immediately, but should be followed through delivery or termination of the pregnancy. Subjects should also notify the investigator if they become pregnant within 28 days following the last dose of study drug. FPHU/Westat also must be notified if a subject becomes pregnant on study.

If a subject is discontinued from the study before completing the specified duration of treatment, they should be encouraged to complete the end-of-study assessments and to agree to report any serious adverse events for 28 days following the last dose of study drug. The date the subject is withdrawn and the primary reason for discontinuation will be recorded on the case report form (CRF).

4.3.2. Replacement of Study Subjects

Subjects who are screened, but do not receive FF-10501-01 will be replaced.

5. STUDY TREATMENT

5.1. FF-10501-01 Investigational Product Description

FF-10501-01 is an oral antimetabolite anticancer drug. It is a competitive inhibitor of IMPDH.

FF-10501-01 is a white powder provided in the form of film-coated immediate release tablets. In addition to FF-10501-01, formulation components include lactose monohydrate, light anhydrous silicic acid, carmellose calcium, hydroxypropyl cellulose, magnesium stearate, hypromellose, titanium dioxide, talc, and carnauba wax. FF-10501-01 is manufactured for FPHU by Patheon (Missisauga, Ontario, Canada) and will be provided by the sponsor (FPHU).

5.2. Study Drug Administration

FF-10501-01 will be provided directly from the drug distribution center designated by FPHU.

Subjects should be scheduled to begin study therapy following completion of Screening. FF-10501-01 will be administered orally at the dose level prescribed per cohort twice each

day (**approximately every 12 hours**). For subjects on the 21-day dosing schedule, treatment will be continuous for 21 days for each 28-day cycle (=1 cycle). See **Appendix A** for drug dispensing guidelines.

A sufficient supply of FF-10501-01 will be dispensed to the subject by the investigator or trained designee for the subject to take on an outpatient basis between visits.

The following instructions should be reviewed with the subject and a written copy of the instructions provided to the subject:

- Take the prescribed dose of FF-10501-01 tablets (either 50 mg or 200 mg or both) by mouth twice each day with the second dose about 12 hours after the first dose.
- Take the tablets with a full glass of water (approximately 8 ounces). Swallow the tablets whole. Tablets should be taken in the fasting state, approximately 2 hours before or 2 hours after a meal.
- Your dose may be reduced if you have side effects. If a dose reduction is required, follow the instructions given by your doctor. Do not reduce the dose unless your doctor tells you to do so.
- If a scheduled dose of study drug is missed and less than 6 hours have passed since the scheduled dosing time, immediately take the missed dose. If more than 6 hours have passed since the scheduled dosing time, do not take the missed dose. Wait and take the next regularly scheduled dose.
- Each day record the number and dosage of tablets taken on the diary card. If a dose is missed, include the reason the dose was not taken.
- Return the diary card to your study doctor at each visit.
- Return opened and unopened bottles in which the tablets were dispensed.
- Adherence with the study treatment regimen must be assessed at each visit by checking the returned drug supply and reviewing the diary card. Study drug therapy must be reported in the appropriate case report form (CRF) module.

5.3. Treatment Duration

Treatment will continue until confirmation of disease progression, unacceptable toxicity, or subject decision to discontinue therapy

5.4. Dosing Delays and Dose Modifications Due to Toxicity

5.4.1. Toxicity Grading Criteria

Toxicity grading is based on NCI Common Terminology Criteria for Adverse Event v 4.03 (<http://evs.nci.nih.gov/ftp1/CTCAE/About.html>).

5.4.2. Instructions Regarding Dose Delays and Dose Modifications

Adverse events considered for treatment interruption and dose reduction will exclude the events assessed by the investigator as exclusively related to underlying disease or medical

condition/concomitant treatment. If treatment must be delayed for reasons other than toxicity, contact the Medical Monitor to discuss the reasons for delay and plans for resuming study therapy.

- Treatment may be delayed up to 14 days. If the subject has completed two cycles and, in the investigator's opinion, is receiving benefit, treatment may be delayed for longer than 14 days and then resumed following a discussion with the Medical Monitor.
- Subjects who experience a toxicity requiring reduction in dose level may continue treatment at the lower dose level until disease progression or unacceptable toxicity. Once the dose has been reduced it may not be escalated to the starting dose.
- See **Appendix B** for FF-10501-01 dose modification requirements.

